Qualitative study: In all, ten focus groups of 8-10 participants purposively selected with one group from each blood donation group category (i) religious organisations, (ii) educational institutions, (iii) corporate institutions, (iv) organised community groups, and (v) walk-in blood donors. The aim of the focus groups is to identify barriers and recommendations for using iron supplementation and nutritional counselling to increase the blood donor pool. These will be gender-sensitive such that there will be two groups of each blood donation category by gender (e.g., 8-10 females, 8-10 males). The female and male focus groups will meet in separate spaces so only one gender will be interviewed at a time. Thus, there is one male and one female group for each donation category.

Quantitative method: Cross-sectional study to determine the prevalence of anaemia among prospective blood donors: There are 2 distinct components of the cross-sectional study: estimation of the proportion of potential donors deferred due to low haemoglobin and the proportion of first-time potential donors who are ID and IDA. The determination of deferral due to low haemoglobin is routinely collected by the NBSG and does not require consent of potential donors in this study. The proportion deferred will be determined using the same donation sites as the other components of the study with an estimated sample size of 600 and resulting margin of error less than 0.04. Consequently, the 95% confidence intervals for deferment prevalence will have a total width of less than 0.08 giving a more precise estimate than the year-to-year variation in the total percentage deferred. Participant consent is needed to draw blood for determination of ID and IDA. We anticipate that 292 participants will consent and be enrolled with resulting margin of error less than 0.057 and total confidence interval width of less than 0.11 for likely values of the prevalence of ID and IDA among first-time potential donors. Thus the ID and IDA prevalence estimates will have comparable precision to the estimated proportion of deferred using all potential donors at recruitment sites.

Parallel groups' trial to assess the acceptability of iron supplementation: Using a non-inferiority design with a non-inferiority margin of 1 g/dL for haemoglobin levels

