at 4 months, a 1-sided alpha level of 0.025, at least 85% power and under the assumption that the true difference in the means is 0.3 requires 262 participants (131 per arm). This number has been increased to allow up to 10% loss to follow-up or iron supplementation for those initially not requiring supplements (such individuals will be excluded from the primary analysis: see Section 12 for further details), thus the sample size is 292. For efficiency, participants will be enrolled into both parts of the quantitative study.

For efficiency, participants will be enrolled into both parts of the quantitative study.

Sample size justification

Cross-sectional study: Since all potential donors will contribute to the estimate of the proportion of potential donors who are deferred due to low haemoglobin, the estimate of this proportion will be sufficiently accurate to allow for comparisons against yearly rates. As stated above, the annual proportion of deferrals from 2015-2018 ranged from 33-53%. If we assume that 5 blood donors attempt to donate each business day, then there should be about 600 donation attempts over the 6-month enrolment period. Table 1 shows values for the prevalence of low haemoglobin, the corresponding margin of error and the corresponding 95% confidence interval. For example, if the prevalence of low haemoglobin leading to deferral is 50% then a 95% confidence interval would be (46%, 53%) which allows for determination of the prevalence in a range that is smaller than the range of yearly estimates. Note: these estimates were obtained using the usual normal approximation to the sampling distribution of a proportion without a continuity correction.

Table 1: Precision of prevalence estimates for low haemoglobin leading to deferral.

| Prevalence | Margin of error | 95% confidence interval |
|-------------------|------------------------|--------------------------------|
| 0.2 | 0.032 | 0.17, 0.23 |

| | | |
|-----|-------|------------|
| 0.3 | 0.037 | 0.26, 0.34 |
| 0.4 | 0.039 | 0.36, 0.44 |
| 0.5 | 0.040 | 0.46, 0.54 |
| 0.6 | 0.039 | 0.56, 0.64 |

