The National Blood Service, Ghana (NBSG) SZBC located in the capital Accra annually collects voluntary blood donations from 200-300 blood donor groups that are categorised as (i) religious organisations, (ii) educational institutions, (iii) corporate institutions, (iv) organised community groups, (v) walk-in blood donors and (vi) mass/media events. Data for the prevalence of deferral assessment will be collected from all prospective voluntary blood donors within the catchment areas of the SZBC. The prevalence study of ID and IDA as well as the parallel groups' trial will be restricted to first-time donors. Generally, prospective voluntary blood donors are healthy, unlikely to be severely anaemic and are more likely to be male.

The study population will be all adults between the ages of 17 and 60 years who visit blood donation sites at the time of recruitment. The lower limit takes into account the lawful requirements of a country for giving consent, the intensified threat of vasovagal reactions in younger donors, and the augmented iron needs of adolescents and young females^{21,22}. The upper age limit is so set because of an increase in various medical conditions with age especially cardiovascular diseases making donations more hazardous²³. A stringent screening and selection process is performed to evaluate the suitability of prospective donors. This is essential to

guarantee the safety and adequacy of the blood supply; protecting the wellbeing of the recipients of transfusion as well as the fitness of the donors while ensuring that qualified donors are not deferred needlessly.

Stratification and Sampling

The SZBC contributes to the blood service needs of the Western, Central, Greater Accra, Eastern and the Volta Regions of Ghana. In 2018 and 2019, the SZBC attended to an average of 550 prospective voluntary blood donors a week, including 80 walk-in donors. Out of this number, the study will recruit all participants (who fall within the inclusion criteria) reporting per day for up to 6 months until the sample size is attained. Eligible participants will form the sampling frame for the study.

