Analytical approaches to the analysis of data from the prevalence study will focus on univariate summaries but will also investigate risk factors for deferral, ID, and IDA. Exact confidence intervals for the probability of deferral, the probability of ID and the probability of IDA will be computed using the method first described by Clopper and Pearson. Logistic regression will be used to assess risk factors for these outcomes. For deferral, these risk factors will include age and sex but likely little else as the data we can obtain for these individuals is limited. For ID and IDA, the role of demographics will be investigated as well as other factors including socio-economic status, medical history, and diet. Final models for the impact of risk factors on deferral, ID, and IDA will include demographics and a selection of covariates found to have a statistically significant univariate association with each of these outcomes.

The analysis for the primary outcome of haemoglobin levels at 4 months will be conducted using a linear model with haemoglobin levels at 4 months as the response variable. It is unlikely that there is a need to transform the response variable as haemoglobin levels are usually symmetrically distributed with tails that decay at rates consistent with the normal distribution. However, if informal univariate assessments of normality (e.g., qq-plots) indicate strong departures from these expectations, the Box-Cox transformation will be used to select a transformation. The set of explanatory variables will be group membership (i.e.,

received iron supplementation or not), baseline haemoglobin, sex, and age. A 1-sided t-test for the regression coefficient associated with group membership will be conducted with a significance level of 0.025 to test the inferiority hypothesis. This analysis will exclude individuals who did not receive iron supplementation at baseline but received it during follow-up due to changes in ferritin or haemoglobin values. The frequency of this will be closely tracked and if more than 10% of participants in the group initially not receiving iron supplementation receive iron supplementation during follow-up, alternative analysis approaches will be considered and presented to the DSMB. At a minimum, sensitivity analyses which include those requiring iron supplementation during follow-up will be pursued. These analyses will include those requiring supplementation during follow-up in each of the 2 groups.

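### The deferral study's source population and its size of 600 are not reconciled, and several stated precision figures for deferral, ID and IDA prevalence are wrong

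*Protocol*

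**What the plan says.** **Size.** Protocol, Sample size justification (repeated in SAP 2.4): "If we assume that 5 blood donors attempt to donate each business day, then there should be about 600 donation attempts". The count refers to the half-year in which participants are enrolled. Protocol, Sample Size, and SAP 1.2 carry this forward as "an estimated sample size of 600 and resulting margin of error less than 0.04", with a total width below 0.08.

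**Population, wide reading.** Protocol, Study site and Population (and the same heading in SAP 1.2): "Data for the prevalence of deferral assessment will be collected from all prospective voluntary blood donors within the catchment areas of the SZBC". Stratification and Sampling gives the flow: "the SZBC attended to an average of 550 prospective voluntary blood donors a week, including 80 walk-in donors".

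**Population, narrow reading.** Protocol, Sample Size, and SAP 1.2 use the same donation sites as the other study components. Protocol, Regimen, records every attempt and deferral at the sites that recruit for the parallel groups trial, over the first 6 months.

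**ID and IDA.** With 292 participants the plan promises a margin below 0.057 and a "total confidence interval width of less than 0.11" for likely prevalences. SAP 2.4 describes Table 2 as precision within deferral strata, with the same entries as the protocol's Table 2.

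**Intervals.** Table 1 rests on the normal approximation, and both documents say so. The protocol's Quantitative Data Analysis plans "Exact confidence intervals for the probability of deferral, the probability of ID and the probability of IDA". SAP 7.1 keeps the exact interval for deferral. For ID and IDA it uses Bayesian post-stratified intervals, weighted by the deferral proportion among first-time donors.

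**The concern.** A reader cannot tell which donors form the denominator of the deferral estimate, or where 5 a day comes from. The two populations may differ in size by more than an order of magnitude, and no passage links them.

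This matters for two estimates. The deferral prevalence is a study component meant for comparison with yearly rates, so its denominator should be fixed in advance. SAP 7.1 then uses the first-time-donor deferral proportion, d, as a weight: overall ID prevalence = d × (ID prevalence in deferred donors) + (1 − d) × (ID prevalence in donors not deferred). A shift in d passes into the overall figure in proportion to the difference between the strata.

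Separately, some printed precision figures disagree with the plan's own tables or method. One table describes strata but uses the whole sample.

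**Working it through.** **Inputs.** 5 attempts per business day; about 600 attempts; 6 months' enrolment (24-26 weeks); 550 voluntary donors a week, 80 of them walk-ins; 292 participants; ID prevalence 41.3% (Sample size justification). Normal margin = 1.96 × √(p(1−p)/n); width = 2 × margin.

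**1. Reproducing the plan.**
- 5 × 120 business days (24 weeks) = 600. At 26 weeks, 5 × 130 = 650.
- At n = 600 the normal margins at 0.2, 0.3, 0.4, 0.5 and 0.6 are 0.0320, 0.0367, 0.0392, 0.0400 and 0.0392. All five Table 1 margins reproduce.

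**2. Throughput under the two readings.**
- All catchment: 550 / 5 = 110 per business day; 550 × 26 = 14,300 (550 × 24 = 13,200). Normal margin at 50%: 1.96 × √(0.25/14,300) = 0.0082.
- Walk-ins alone: 80 / 5 = 16 per business day; 80 × 26 = 2,080. Margin at 50%: 0.0215.
- As assumed: 5 per business day; 600; margin at 50%: 0.0400.
- Plausibility check: the plan needs almost 2.5 consents a day. At 5 attempts a day, 2.5 / 5 = half of all attempts would have to come from eligible first-time donors who consent, yet the same section says only a subset are first-time donors.

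**3. The 50% example.** 0.50 ± 0.040 = (0.460, 0.540). Table 1 agrees; the text in both documents prints (46%, 53%).

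**4. ID/IDA width at n = 292, normal method.**
- p = 0.30: 0.105
- p = 0.40: 0.112
- p = 0.413 (the plan's ID figure): 0.113
- p = 0.50: 0.115

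The width reaches 0.11 when p(1−p) ≥ 292 × (0.055/1.96)² = 0.230, that is, for p from about 0.36 to 0.64. The limit holds at the plan's IDA figure of 30.7% (0.106) but not at its ID figure.

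**5. Table 2 within strata.** The printed margins are those for n = 292, the total over both strata. The documents give no stratum sizes. Assuming an equal split, n = 146 each:
- p = 0.30: 1.96 × √(0.21/146) = 0.074 (printed 0.053). The SAP's example becomes about (23%, 37%) instead of (25%, 35%).
- p = 0.50: 1.96 × √(0.25/146) = 0.081 (printed 0.057).

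**6. Exact interval for deferral at n = 600 (Clopper-Pearson), total width.**
- p = 0.30: 0.0749
- p = 0.40: 0.0799
- p = 0.45: 0.0811
- p = 0.50: 0.0815
- p = 0.53: 0.0814
- p = 0.60: 0.0799

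The width exceeds 0.08 only between about 0.40 and 0.60. The largest margin is 0.0408, and about 623 attempts would bring the worst case under 0.08.

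**The case against.** The strongest reply is that 600 is a planning assumption for a subset of the zone. The sample size text is conditional and approximate, and both documents tie the 600 to the study's donation sites. This stands as far as it goes: a reader might infer that 14,300 flatly contradicts 600, and the documents do not support that. The reply does not remove the second population named under Study site and Population, nor supply a source for 5 a day.

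A reader might also infer that recording stops at 600, which would be 600 / 550 = 1.1 weeks of SZBC volume. No such rule exists. Regimen records all attempts at recruitment sites over the first 6 months, so a larger flow would simply give better precision.

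Nor should 14,300 be adopted as the planned size. It is 2018-2019 attendance, before inclusion items 1-3, which the protocol applies to the deferral study, and the protocol was written with Covid-19 measures in place. SAP 3.4 and 7.1 also record donor type, replacement/family or voluntary, in the deferral study, so even "all voluntary donors" may not match the SAP's denominator.

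Finally, it is tempting to say that the exact intervals miss the stated limits at 600. They do so only for prevalences of about 0.40-0.60, by less than 0.001 in the margin, and Table 1 discloses its method. The plan does not give an expected deferral rate among attempts: the 33-53% is described in the Problem Statement as the low-haemoglobin share of deferred donors.

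**Conclusion.** The point holds as a failure to reconcile population and size, together with specific errors in stated precision.

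- **Population and size.** Two source populations stand side by side in both documents. The 5 a day is unsourced and below the 16 walk-ins per business day, although the comparison with walk-ins bites only if the walk-in stream recruits. The deferral margin at 50% is 0.040 at 600 and about 0.008 at the all-catchment upper figure. Any error in the expected number is therefore probably in the favourable direction; the substantive issue is which donors define the estimate and the ID/IDA weight. That weight uses first-time donors only, so its margin is wider than one computed from all attempts.
- **Wrong figures, no assumption needed.** (46%, 53%) should be (46%, 54%). The ID/IDA width is 0.113 at 41.3% and up to 0.115 at 50%, not below 0.11.
- **SAP Table 2.** The margins are too small for the strata it describes. The size of the error depends on the split; 0.074 and 0.081 rest on an assumed 146 per stratum, and the smaller stratum fares worse if the split is unequal.
- **Exact interval at 600.** A width up to 0.082 is a minor correction with no practical effect.

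**What to change.** 1. State one source population for the deferral estimate, in the same words, in the protocol's Sample Size, Study site and Population, and Regimen sections and in SAP 1.2. Say whether replacement/family donors are counted.
2. Derive the expected number of attempts from that population's throughput after inclusion items 1-3, cite the source, and restate the margin. Use 14,300 (margin about 0.008) only as the upper figure under the all-catchment reading. Give the expected number of first-time donors as well, since they supply the weight in SAP 7.1.
3. Correct the 50% example to (46%, 54%) in both documents. Replace the ID/IDA width below 0.11 with about 0.113 at 41.3% and up to 0.115 at 50% (normal method, n = 292).
4. In the SAP, recompute Table 2 and its example with the expected stratum sizes. Substituting exact intervals at n = 292 would not cure it: the SAP no longer plans that interval for ID and IDA, and 292 is not a stratum size.
5. Optionally, note that the exact deferral interval at 600 has a width up to 0.082.

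The cost is wording, two recomputed tables and a throughput count from data that the blood service collects routinely without study consent. No participants or procedures are added.

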Out of the sampling frame, participants will be purposively sampled for Focus Group Discussions (FGDs). In all there will be ten FGDs i.e. two groups (male-only and female-only) randomly selected to represent each of the five NBSG voluntary blood donation categories (excluding mass/media event donors), and with each group composed of both first-time and repeat donors. In-depth interviews will also be conducted with blood donation staff and medical officers responsible for blood donation.

Regimen

The prevalence study will be conducted over the first 6 months of the study period. For the cross-sectional deferral assessment, all donation attempts and deferrals from sites where recruitment for the parallel groups study will take place will be recorded. The number of deferrals among first-time donors will also be determined. Potential first-time donors will be asked if they are interested in participating in a study of the prevalence of ID and IDA and the impact of iron supplementation on haemoglobin levels and repeat donation. Those who express interest and consent to the study will be asked to return in approximately 2 weeks. During this 2-week period a full blood count (FBC) and plasma ferritin measurement will be determined, and participants will be classified as ID, IDA or otherwise (which we refer to as controls in this protocol). Those found to be ID or IDA will receive oral

iron supplementation and nutritional counseling. Controls will not be given iron supplementation but will receive the standard practice of nutritional counseling for blood donors. Additional baseline data will be collected at the 2-week return visit. The duration of the intervention period is 4 months with two interim visits (approximately 2 months apart) and a final visit at 6 months. A blood draw will be conducted for a FBC, peripheral film comment, malaria rapid test and ferritin measurement at both interim visits and the final visit. Participants will receive bi-weekly follow-up phone calls for adherence and monitoring for adverse events. Qualitative assessment of acceptability of oral iron supplementation among donors previously deferred will be performed during the final month of the pilot study.

Inclusion Criteria

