Demography and social characteristics of participants

- Name: _____
- Name of Community (Group): _____
- Age: _____
- Sex: _____
- Highest Educational level attained: _____
- Religion: _____
- Ethnic background: _____
- Occupation: _____

You participated in this project, which involved blood donors.

- How did the project influence your knowledge about iron supplementation for deferred blood donors?

Probe:

- *Are you aware of any cultural reasons why people do not use iron supplements?*
- *Are you aware of any religious reasons why people do not use iron supplements?*
- *Did it increase your awareness of iron supplements?*
- *Did it improve your knowledge on the usefulness of iron supplements?*
- *Do you believe people will like to use iron supplements after the project?*

- How did the project influence your attitudes to iron supplementation for deferred blood donors?

Probe:

- *Are you aware of any cultural reasons why people do not use iron supplements?*
- *Are you aware of any religious reasons why people do not use iron supplements?*
- *Did it increase your attitude to use of iron supplements?*
- *Do you believe people will like to use iron supplements after the project?*

- How did the project influence your beliefs about iron supplementation for deferred blood donors?

Probe:

- *Are you aware of any cultural beliefs why people do not use iron supplements?*
- *Are you aware of any religious beliefs why people do not use iron supplements?*
- *Did it influence your beliefs (either positively or negatively) of iron supplements?*
- *Do you believe people will like to use iron supplements after the project?*

- What influenced your participation in this project?

Probe:

- *Was the colour of the iron supplement culturally acceptable?*
- *Was the dosage of the iron supplement culturally acceptable?*
- *Did taking these supplement affect your participation, negatively or positively?*
- *Was there in any religious and cultural aspects of your life that affected how you participated in the project generally?*

- Please describe the counselling you received about iron supplementation?

Probe:

- *Were you given adequate information and guidance on eating iron or micronutrient-rich foods?*
- *Were any cultural or religious concerns or inhibitions to eating these foods addressed?*

- *Were there issues you did not understand during the counselling sessions?*
- *Were there issues you disagreed with during the counselling sessions?*

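### Focus groups must include repeat donors, who are barred from the trial, and no iron-exposure criterion is set, so an unknown and possibly large share of respondents will not have taken the supplement the guide asks about

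*Protocol*

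**What the plan says.** Protocol, Sample Size: "In all, ten focus groups of 8-10 participants purposively selected", one male and one female group for each of five donation categories. Protocol, Stratification and Sampling, adds the donor mix: "with each group composed of both first-time and repeat donors". SAP 1.2 repeats this. Neither document mentions arm or receipt of iron as a selection criterion.

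Protocol, Study site and Population: "The prevalence study of ID and IDA as well as the parallel groups' trial will be restricted to first-time donors". Exclusion criterion 2 in both documents removes anyone who reports a previous donation from the ID/IDA study and the trial.

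Protocol, Regimen, names a third population: "Qualitative assessment of acceptability of oral iron supplementation among donors previously deferred will be performed during the final month of the pilot study". The SAP does not carry this sentence.

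The discussion guide (Protocol, Appendix 1) opens its main questions with "You participated in this project, which involved blood donors". Its probes include "Was the dosage of the iron supplement culturally acceptable", with others on the supplement's colour, the effect of taking it and the counselling received about iron.

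**The concern.** Three descriptions of the respondents do not match. The sampling text wants first-time and repeat donors, the Regimen text wants previously deferred donors, and the guide addresses people who were in the project and used the supplement. Only the third group can report what it was like to take iron three times a week.

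Acceptability is part of the primary objective and is secondary outcome D. Both documents say the focus groups will guide the UH3 phase. If people who never took the supplement answer the questions about taking it, hypothetical opinion may be reported as user experience, and problems specific to taking iron may be missed. This cannot be recovered once the discussions have been held.

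**Working it through.** **Who can have taken study iron.** A repeat donor, read as someone who donated before screening, can belong only to the deferral component. That component uses routinely collected data without study consent (Protocol, Sample Size). Such a person has no study iron and no study visits. Within the trial, the intervention arm is assigned iron at enrolment. Controls receive it only if a follow-up visit shows iron deficiency or low haemoglobin (Protocol, Follow Up Assessments; SAP 4).

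**Deferral is not the same as exposure.** Iron is given whatever the deferral status (Design, both documents). A donor who passes copper sulphate but has ferritin below 15 µg/L receives iron without having been deferred. A woman with haemoglobin between 11.5 and 12.0 g/dL and normal ferritin can be deferred by copper sulphate (cut-off 12.0) and still be a control, since the anaemia threshold for women is 11.5. The Regimen sentence therefore does not supply the missing criterion.

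**Which guide items need exposure.** Colour, dosage and the effect of taking the supplement do. Counselling about iron needs at least trial participation. Knowledge, beliefs, barriers and recommendations do not need exposure.

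**Size.** The documents give no figure for the exposed share, so there is none to reproduce. Inputs:

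- Respondents: 10 groups × 8 to 10 = 80 to 100 (Protocol, Sample Size).
- Arms: equal numbers planned (Design).
- r, the repeat-donor share: not stated; assumed 10%, 25% and 50%.
- x, the share of controls later given iron: not known; assumed 0%, 10% and 20%. Both documents would consider another primary analysis above 10%.

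If sampling ignores arm, the share ever given study iron = (1 − r) × (0.5 + 0.5x).

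| r | x = 0% | x = 10% | x = 20% |
|---|---|---|---|
| 0% | 50% | 55% | 60% |
| 10% | 45% | 49.5% | 54% |
| 25% | 37.5% | 41% | 45% |
| 50% | 25% | 27.5% | 30% |

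For example, r = 25% and x = 0 gives 0.75 × 0.5 = 37.5%. At r = 50% and x = 0, 25% of 80 to 100 is 20 to 25 people, or 2 to 2.5 per group.

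The share falls below one half once r exceeds x/(1 + x): any r above 0 when x = 0, above 9.1% when x = 10%, and above 16.7% when x = 20%.

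If the team instead drew every first-time member from the iron arm, the share would be 1 − r: 90%, 75% and 50% at the same three values of r. The plan permits either approach.

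**The case against.** The case on the other side has five parts.

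- *Focus groups are one source among several.* The Protocol's acceptability objective also uses the safety comparison, questionnaires and key informant interviews. SAP 7.2.2 defines participant acceptability by SAEs, grade 3 or 4 AEs and known adverse reactions, and it collects adherence items. This stands. A reader might infer that the acceptability finding as a whole would rest mainly on non-users, and the documents do not support that. Still, the Protocol's item-level analysis of acceptability questionnaires is not carried into SAP section 7, and the in-depth interviews are with blood donation staff and medical officers. The focus groups therefore remain important for participants' non-safety views.
- *Sampling is purposive.* The team may intend to select iron users, and the Regimen sentence leans towards donors with low haemoglobin, many of whom receive iron under the SAP. This is possible, but neither document says so, and deferral does not guarantee exposure.
- *Repeat donors is undefined.* The schedule places the qualitative assessment at the final visit, and repeat donation within 6 months is a trial outcome, so the term could mean trial participants who have since donated again. The conflict with the exclusion would then disappear. The missing exposure criterion would remain, with about half exposed under arm-blind sampling (the r = 0 row).
- *The guide allows for mixed experience.* Its closing section counts how many members have donated and how many have used iron after donating, and controls do receive nutritional counselling. That section gathers composite group views, however, and the respondent details have no field for arm or iron receipt.
- *Repeat donors belong there.* Barriers to repeat donation are a secondary objective. This stands and is a reason not to remove them.

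**Conclusion.** The mismatch is in the text of both documents. Focus groups must include donors who, on the plain reading, could not have been in the trial. No criterion secures iron users, and the guide presumes participation and use. The Protocol's statement about previously deferred donors adds a further population that fits neither.

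The exposed share is unknown and could be low: 45%, 37.5% or 25% at r = 10%, 25% or 50%, assuming arm-blind sampling, equal arms and no later iron for controls. It is somewhat higher if controls cross over.

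A reader might infer that most respondents will be unable to answer the questions on taking iron. The plan does not establish this. It depends on a repeat-donor share that the plan does not state and on selection that ignores arm. One of the arm-blind scenarios with r above 0 gives 54%, and selection from the iron arm could give up to 90% at r = 10%. Many guide items can also be answered without exposure. The point is worth correcting because the remedy is mainly wording and the loss would be irreversible.

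**What to change.** In Protocol, Stratification and Sampling and Regimen, and in SAP 1.2 and 6:

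1. Define repeat donors, and reconcile the group composition with the Regimen sentence on previously deferred donors.
2. Add receipt of study iron as a purposive sampling criterion, so that each donation category includes participants who received it, among them low adherers and people who stopped.
3. Record each respondent's arm and iron receipt. Ask and report the iron-experience items only among recipients.
4. Report the views of controls and repeat donors separately, as prospective views. Repeat donors may stay in for the repeat-donation objective.

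Restricting all ten groups to the iron arm is not needed and may not be feasible. Five female groups of at least 8 would need 40 women from about 146 iron-arm participants (292/2), or 27%, spread evenly over five categories with full attendance. The Protocol says donors are more likely to be male and gives no female share.

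Cost: changes to the wording and the guide, with the same ten groups and sessions. Non-recipients would have fewer places, and recruiting and reporting by exposure takes slightly more work.
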